1. INTRODUCTION

Noncommunicable diseases are responsible for about 41 million deaths/year, which is equivalent to 71% of deaths worldwide ¹. It is no different in Brazil, chronic diseases represent the main challenge in health, about 72% of deaths in the country are due to chronic non-communicable diseases, which represent 75% of the expenses of the Unified Health System (SUS) - Figure 1 .

[figure not shown]

Figure 1 . Chronic diseases represent the main health challenge in Brazil.

The World Health Organization's 2030 Agenda for Sustainable Development reveals the commitment of member countries to a 30% reduction in premature mortality from non-communicable diseases, especially cardiovascular diseases (ischemic heart disease and stroke), cancer, respiratory disease and diabetes ².

Cardiovascular diseases represent one of the major causes of morbidity and mortality worldwide, which has encouraged numerous researches in different areas. Around 17.5 million people die from cardiovascular diseases annually worldwide, according to data from the World Health Organization (Figure 2). Only in Brazil, diseases related to heart problems correspond to about 300,000 deaths per year. They are chronic and can be treated clinically or surgically³.

Figure 2 . Leading causes of death worldwide in the year 2019.

Source: WHO Global Health Estimates.

A significant portion of cardiovascular diseases require surgical treatments, with myocardial revascularization surgeries, correction of valve diseases, followed by surgeries to correct aortic diseases and congenital heart diseases, the most common in adults and the elderly. These patients are usually referred to the operating room with different comorbidities, subject to more complications in the

intra and postoperative period, which leads to an increase in hospital stay and monetary and technological costs invested in their treatment and recovery ^{4,5}.

Brazil is the second country in the world in number of heart surgeries performed, totaling around 100,000 surgeries/year, second only to the USA, which performs around 300,000 surgeries/year.

There are over 320 million inpatient surgical procedures performed worldwide. Recently, the *International Surgical Outcomes (ISOS) Study (ISOS Group 2016)* highlighted that about 17% of these patients develop one or more complications and, among them, 2.8% die as a result of them ^{6,7}.

The postoperative period of cardiac surgery requires continuous observation from the health team, quick decision-making and highly complex care. This period presents many challenges for the multidisciplinary team, due to the need for intensive/constant monitoring and the potential postoperative complications. In addition to the lives lost, these postoperative complications dramatically increase hospital and healthcare costs ⁸.

One of the most frequent complications in the postoperative period of cardiovascular surgery are arrhythmias, with atrial fibrillation being the most frequent arrhythmia in the postoperative period ⁹. The prevalence of postoperative atrial fibrillation (POAF) varies between 15 and 40% in coronary artery bypass grafting procedures, 37 to 60% in valve surgery and more than 60% in combined interventions and 24% in patients undergoing heart transplantation.

In 90% of cases, POAF appears in the first four postoperative days ¹⁰. The average length of the first episode is 7-8 hours. Recurrence occurs in 40% of cases and occurs within the first 24 hours. Up to 80% of patients remain in sinus rhythm

24 hours after the first episode. About 14% of patients with atrial fibrillation after cardiac surgery (AFACS) remain with this rhythmic disorder for up to two weeks ¹¹.

Other emerging evidence suggests that POAF is associated with long-term sequelae such as stroke, heart failure, and all-cause ¹²mortality.¹³

Despite the advances in the area and the different methods for monitoring POAF, there is still no method that allows the automated evaluation of fibrillation episodes for a very prolonged period. Thus, the detection of POAF becomes an important challenge.

Wearable devices such as *smartphones* and *smartwatches*, are a great promise for screening and monitoring AF, and can present up to 93% sensitivity and 84% specificity when compared to standard ECG ¹⁴. In addition, they are easy to use and allow evaluating the possible adherence of patients to this new modality of assisted telemonitoring. However, to be used as a medical device, these *wearables* need to be accurate in outpatient settings.

Technological resources for health solution

The use of terms such as Internet of Things or *Internet of Things* (IoT), Internet of Everything or *Internet of Everything* (IoE), cloud computing, cyberculture, big data, artificial intelligence, neural networks, wearable devices, among *others* , are already part of our daily lives as innovative technological contributions in the area of health ^{15, 16}.

Wearables are proving to be very effective tools with regard to the prevention, detection or even management of chronic diseases, according to Baig et al ¹⁷. The use of *wearables* to monitor vital signs, such as oxygen saturation (SpO₂), heart rate, blood pressure and respiratory rate is of fundamental

importance ¹⁸. In addition, the possibility of generating early warnings in case of clinical instability of the patient was associated with a significant decrease in the number of cardiac arrests and deaths ¹⁹. Statistical data and trend models, even generated from non-medical devices such as *wearables*, are of great value in preventive and predictive actions in health care ^{20, 21}.

The use and implementation of any new technology comes at a cost that must be balanced against the potential savings associated with the expected improvement in postoperative recovery. Postoperative complications are expensive to treat and prolong hospital stays. However, the use of such resources as *wearables* will allow a variety of data to be collected by sensors and allow for earlier interventions ²².

Recent data from a GFK36 global survey on *wearables*, involving more than 20,000 people in 16 countries, found that around 33% use tracking to monitor their health, through apps, bracelets, smart watches and clips. Among those interviewed, 18% had already used the technology some time ago, 45% had never used it and 4% were unable to answer. This survey revealed an interest in wellness, looking for information about exercise, calorie consumption, and even sleep. Another interesting data from this survey is that Brazil occupies, alongside the United States, the second position in the use of health and physical condition monitoring, losing to China and ahead of Germany and France ²³.

In this context, the use of available technologies can be used as strategies for faster dehospitalization, with remote monitoring of the patient, since the initial application of *wearables* in surgery may eventually allow better communication and decision-making by the care team through the collection, interpretation and

presentation of patient-specific measurements relevant to the context of the disease ²⁴.

Wearable devices, such as *smartwatches*, can be an innovative and relevant alternative, making it possible to reduce hospitalization periods and the early return of patients to their routine activities safely, in an assisted way.

Integration of wearable technology health data with the electronic record

Currently, Information and Communication Technology (ICT) tools are present in practically all activities related to the health area, such as teaching, research or assistance.

There is evidence that a feasible and adequate electronic health record (EHR) helps professionals in decision-making in patient health care, improving safety and efficiency of care ²⁵. In view of this, there has been a progressive interest in the medical field in using data captured from the RES, as they contain variables with valuable information, such as demographic data, diagnoses, medications and laboratory data ^{26, 27}.

However, although electronic records serve different purposes and utilize different IT system architectures, there are many operational challenges and technical issues. However, the different needs and subdivisions of the health area, without a systematic view, end up using an exaggerated amount of software and spreadsheets, without interconnection or integration, making it difficult or even preventing the communication and transformation of data into relevant information and knowledge in practice. clinic ^{28, 29}.

InCor's electronic medical record (Integrated Information System InCor - SI³) provides integrated data from the Clinical Information System via a standard web

interface, which allows independence from the hardware platform *used* for access, in addition to providing better management of health resources in the institution, whether in supplies, occupation of beds, laboratory management, medications, costs of procedures and information that can be obtained in real-time through standardized interfaces ³⁰. Currently, more than 1.4 million patients are registered in SI3 with all their care data, resulting in more than 500 Terabytes of data. The systems range from scheduling appointments and exams and admitting patients to bed control, laboratory management, medication, supplies and billing to the SUS.

In this way, not only the secure integration of the currently existing databases, but also the coherent use of the stored information, provide a valuable source of knowledge for a better understanding of patients treated by the SUS, thus allowing exploratory, prospective and retrospective studies to produce predictive models, and facilitating decision-making for better management of public health policies.

Wearable technology, such as the use of *smartwatches*, can capture valuable bioparameters, and that at the same time, EHR provides practical platforms for including these data - the creation of a graphical interface that displays patients' health data from these devices could both transform medical care and ensure patient privacy.

In view of the above, the present study aims, through the use of the **Smartwatch SAMSUNG™ Galaxy Watch5**, to validate a measurement model and data analysis that early indicate the need for medical assistance due to atrial fibrillation (AF) in individuals with heart disease undergoing cardiac surgery, as well as to evaluate patients' commitment to a new monitoring routine using regular

alerts based on automated readings, in comparison with the traditional postoperative routine.

The use of such devices as predictors of cardiac alterations could save the SUS hundreds of millions of reais per year, as it would avoid events in these individuals and, consequently, their treatment. To this end, this study will be randomized so that 50 patients will use a **Smartwatch device SAMSUNG™ Galaxy Watch5** and 50 patients will follow the institution's standard treatment (not monitored by wearables).

2. OBJECTIVES

2.1 Primary Purpose

telemonitoring platform using the **Smartwatch SAMSUNG™ Galaxy Watch5**, validating its applicability in patients with POAF.

2.2 Secondary objectives

- Evaluate the accuracy of the **Smartwatch SAMSUNG™ Galaxy Watch5** in detecting vital signs through optical sensors and, in particular, possible heart rhythm irregularities.
- Compare the results of the variables heart rate, blood pressure and peripheral oxygen saturation (SpO₂) and electrocardiogram provided by the **Smartwatch SAMSUNG™ Galaxy Watch5** with data obtained from gold standard reference equipment.

3. METHODOLOGY

3.1 Place of study

This project will be carried out entirely on the premises of the Instituto do Coração of the Hospital das Clínicas of the Faculty of Medicine of the University of São Paulo. The sample will consist of 100 outpatients, with heart disease undergoing cardiac surgery, and selected during the pre -surgical consultation. The sample size was proposed by the contractor because it is a pilot study to evaluate the accuracy of the equipment in a sample with POAF.

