3.4 Selection of volunteers

Patients with heart disease undergoing cardiac surgery, monitored at the InCor outpatient clinic. Randomization will be performed 1:1 using an electronic randomization system and subsequently stratified from the RedCap platform, without knowledge by the team involved in the study. Patients will be randomized to intervention group (teleassisted group) or control group (standard follow-up of the institution)

1. **Control group (N=50):** patients with heart disease who underwent a surgical procedure with standard outpatient and post-surgical follow-up, according to institutional routines and protocols;
2. **Tele-assisted group (N=50):** patients with heart disease undergoing a surgical procedure remotely monitored through *smartwatch* and application.

Adult patients will be included, of both sexes, and ethnic profile representative of the Brazilian population, characteristic of the user population of the Unified Health System (SUS).

re-hospitalization rate, through scheduled consultations and extra interurrences (clock x institutional standard). As secondary outcomes will be evaluated: technological and treatment adherence, through the use of the mobile application by patients and development and implementation of the telemonitoring platform.

The goal is the inclusion of 40 patients/month (in all, in the 2 study groups: Remotely monitored watch group and group without a watch, following the institutional standard, following the randomization order generated by a specific

system) with 20 in each group of the study. In addition, the inclusion of patients will happen gradually and continuously, with 1 patient per group/working day.

Sem 1	Sem 2	Sem 3	Sem 4	Sem 5	Sem 6	Sem 7	Sem 8	Sem 9
1 ao 5	6 ao 10	11 ao 15	16 ao 20	21 ao 25	26 ao 30	31 ao 35	36 ao 40	41 ao 45
						1 ao 3	4 ao 8	9 ao 13
Sem 10	Sem 11	Sem 12	Sem 13	Sem 14	Sem 15	Sem 16	Sem 17	
46 ao 50								
14 ao 18	19 ao 23	24 ao 28	29 ao 33	34 ao 38	39 ao 43	44 ao 48	49 ao 50	
● Inclusão ● Retorno								

Figure 3. Flow of inclusion of patients in each arm of the study.

The remote patient monitoring flowchart to be used in this project is shown in Figure 3. Briefly, it includes:

1. Preoperative outpatient consultation with complete anamnesis to verify eligibility for using the **SAMSUNG™ Galaxy Watch5 Smartwatch**;
2. Hospitalization, surgery and collection of intraoperative data;

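### Section 3.1 presents the accuracy sample as one with POAF, but the design yields a sample at risk of POAF; with wearers only, the paired ECGs are unlikely to support a claim of validated accuracy in POAF

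*Combined protocol and SAP*

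**What the plan says.** **Sample.** Section 3.1 sets 100 patients, a number put forward by the contracting company because "it is a pilot study to evaluate the accuracy of the equipment in a sample with POAF". The same section has the patients "selected during the pre -surgical consultation". Table 1 (Section 3.5) also allows entry after admission, but still before the operation. Sections 3.2 and 3.3 contain no POAF requirement.

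**Aims.** Section 2.1 speaks of "validating its applicability in patients with POAF". The Introduction aims to "validate a measurement model and data analysis that early indicate the need for medical assistance due to atrial fibrillation (AF". Section 2.2 makes accuracy "in detecting vital signs through optical sensors and, in particular, possible heart rhythm irregularities" a secondary objective.

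**Who wears the watch.** The tele-assisted arm of 50 is described in Section 3.4 as "patients with heart disease undergoing a surgical procedure remotely monitored through" watch and application. The Introduction puts the other 50 on "standard treatment (not monitored by wearables".

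**Reference ECG.** Table 1 and the section on traditional versus smartwatch ECG place the watch/12-lead comparison in Phase 3. Neither names an arm, a day or a number of pairs per patient. In Phase 5, SpO2 and blood pressure each have a reference method, whereas ECG lists the watch alone, with a report on whether the watch's classification is confirmed. Remote-phase ECGs are manual watch recordings.

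**Analysis.** Section 3.6 offers parametric or non-parametric tests chosen by normality, at p<0.05. It names no sensitivity, specificity or confidence interval.

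**The concern.** The one scientific reason given for the sample is a property that the design does not supply. Nobody can have POAF at a pre-surgical visit, and no later step selects those who develop it. What counts for AF accuracy is the number of patients in POAF when the watch and the 12-lead ECG are recorded together, and the plan neither states nor estimates that number.

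If it is small, a report could claim validated accuracy in POAF on a handful of positive traces. The analysis section would not expose this. AF yes or no is categorical, so a normality check does not apply to it, and a p-value does not measure accuracy.

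**Working it through.** **The plan's own figure.** The 100 cannot be reproduced, because no precision, power, effect size or expected number of AF cases is given.

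**Inputs, all from the Introduction and used as a rough guide**
- POAF incidence: 15% (lower end, bypass surgery) to 60% (upper end, valve surgery). Combined surgery is put above 60%, with no ceiling.
- Share of POAF cases still in AF: 14% persist for up to two weeks. Up to 80% are in sinus rhythm 24 hours after the first episode, which leaves 20% or more. Neither is a prevalence on a known day.
- Onset: "In 90% of cases, POAF appears in the first four postoperative days", so 10% are late.

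**Assumptions, not in the plan.** One pair per patient, taken near discharge. The only timing limit is the exclusion, in Section 3.3, of stays beyond 14 days.

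**Expected number in POAF at the pair** = N × incidence × share still in AF
- 50 wearers, low: 50 × 0.15 × 0.14 = 1.05
- 50 wearers, high: 50 × 0.60 × 0.20 = 6.0
- 50 wearers, high, with every late onset counted as in AF at the pair: 50 × 0.60 × (0.90 × 0.20 + 0.10) = 8.4
- 100 patients (both arms paired): 2.1 to 12.0, or 16.8 with all late onsets

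At the low end the probability per wearer is 0.15 × 0.14 = 0.021, so the chance of no POAF pair at all is (1 − 0.021)^50 = 35%. At 0.60 × 0.20 = 0.12, the chance of 10 or more is 7%.

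**Precision of sensitivity** (exact Clopper-Pearson 95%). With all n cases detected, the lower bound is 0.025^(1/n).

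| Detected / in POAF | 95% interval |
|---|---|
| 1/1 | 2.5% to 100% |
| 6/6 | 54% to 100% |
| 8/8 | 63% to 100% |
| 7/8 | 47% to 99.7% |
| 17/17 | 80% to 100% |
| 16/17 | 71% to 99.9% |

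**More favourable inputs, 50 wearers, late onsets counted**
- 30% still in AF (assumed): 30 × (0.90 × 0.30 + 0.10) = 11.1. Lower bound for 11/11: 72%.
- Every wearer develops POAF, 20% still in AF: 50 × 0.28 = 14. Lower bound for 14/14: 77%.

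**Specificity.** At about the 84% that the Introduction cites for wearables, 41/49 gives 70% to 93% and 35/42 gives 69% to 93%. It therefore stays estimable across the range of 1 to 8 POAF cases.

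**The case against.** The phrase in Section 3.1 may only mean a sample in which POAF occurs. On the Introduction's rates, 50 × 0.15 = 7.5 to 50 × 0.60 = 30 wearers would develop it at some time. The text reads as a translation, and the sentence in Section 2.1 lacks its beginning in the available copy, so little should rest on it. This stands, and it is a reason to restate the sample rather than enlarge the trial.

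A reader might infer that the trial promises a POAF sensitivity and is too small to deliver it. The documents do not support that: sensitivity is not a named endpoint, no precision target is set, and the study is labelled a pilot. Section 3.4 lists re-hospitalization, adherence and platform implementation as outcomes. The pilot label explains the missing sample size calculation. It does not explain why the sample is described as something it is not.

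A reader might also take 1 to 6 as the protocol's own figure. It is not, since it depends on assumed timing, one pair per patient and pairing of wearers only. The ECG section uses a plural for the tests, so serial pairs are possible. No arm is named, so pairing of all 100 is possible. Incidence above 60% would add POAF cases. Pre-existing AF is not excluded and the CRF records it, so it could add AF traces, but these are not POAF.

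Physician review of remote and Phase 5 watch traces could supply further AF traces. It checks the watch's label on its own recording and is not agreement with the 12-lead reference.

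Lastly, Table 1 assigns the definition and justification of the statistical tests to Phase 6. That qualifies the criticism of Section 3.6, but late definition does not itself supply an accuracy measure or an interval.

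**Conclusion.** The mismatch rests on the text alone: the sample is described as having POAF, while entry is before surgery and POAF is never required. The size is conditional. With wearers only, one pair each near discharge and the Introduction's rates as a rough guide, about 1 to 6 POAF pairs are expected (up to about 8), and perfect detection would leave a lower bound of at most 54% to 63%. Pairing both arms weakens the conclusion: about 2 to 12 (up to about 17), with a lower bound of 80% at best.

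The study can describe AF detection, and can estimate specificity and the agreement of heart rate, blood pressure and SpO2. With wearers only, it is unlikely to support a claim of validated accuracy in POAF. It would go too far to say that the accuracy aims fail as a whole or that more patients are required. Confidence is medium, because the number, day and arm of the ECG pairs are not stated.

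**What to change.** 1. **Section 3.1.** Describe the accuracy sample as cardiac surgery patients at risk of POAF. State whether 50 or 100 patients have the paired ECG. Give the expected number in AF at pairing as conditional on stated assumptions (pairs per patient, timing, incidence, share still in AF).
2. **Section 3.6.** For AF classification, replace the normality-driven tests with sensitivity and specificity against the 12-lead ECG, with exact 95% confidence intervals, reported descriptively. Separate POAF from pre-existing AF. State that no claim of validation in POAF will be made if few AF pairs accrue.
3. **Phase 5 (Table 1).** Report physician review of the watch traces as review of the watch's classification, not as agreement with the 12-lead reference.

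Cost: protocol and analysis text only, with no extra patients or visits. The downside is that the stated accuracy sample may fall from 100 to 50 and the POAF claim becomes less favourable.

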3.2 Inclusion criteria

- Be at least 22 years old;
- Parameters for surgical indication, in the presence of heart disease (mitral or aortic valve disease, coronary artery disease or aortic disease);
- Agree to adhere to the study's procedures and requirements;
- Be able to consent to their participation in writing;
- Possess home internet connectivity infrastructure;

3.3 Exclusion criteria

- Not having undergone cardiac surgery;
- Presence of post-surgical complications with prolonged hospital stay for more than 14 days from surgery date;
- Presence of a Peripherally Inserted Central Catheter (PICC) or limb preservation and cardiac pacemaker in case of impediment to acquisition of the ECG (smartwatch);
- Patients with arteriovenous fistula;
- Presence of skin pathology or skin diseases such as vitiligo, lupus and atopic dermatitis, as well as tattoos in the wrist region, which may interfere with the reading by the optical sensor;
- Show sensitivity or allergic reactions, to any degree, to the component materials of the wearable device;

Volunteers who meet the research inclusion criteria will participate in the study protocols after signing the informed consent form (TCLE).

